3.3.10 Maximal ergometer cycle test

“The sessions will consist of an incremental exercise test on a cycle ergometer to determine $\dot{V}_{O_2\max}$. Initial workload will be set at 35 W and workload will increase by 15 W with each 1 min stage until volitional fatigue. Breath by breath data will be collected and analysed every 5 s using a metabolic system that will be calibrated with room air and standardized gas. The slope of ventilation relative to carbon dioxide production (\dot{V}_E/\dot{V}_{CO_2}) will be calculated with values from rest to maximal exercise. $\dot{V}_{O_2\max}$ will be considered to be achieved when two of the following criteria will be met: an increase in oxygen consumption of less than 100 ml min⁻¹ with a further increase in workload, respiratory exchange ratio (RER) greater than 1.1 or achievement of age-predicted maximal heart rate. Pulse oximetry oxygen saturation (S_{PO_2}) will be continuously monitored with a finger pulse oximeter.” [Med Sci Sports Exerc. 2017 Oct;49\(10\):2131-2138.](#)

3.3.11 Serum proteomics analysis

The discovery of differentially expressed protein profiles in e-cigarettes users and its potential reversibility after e-cigarette cessation might be helpful to better understand the physiopathology of tissue hypoxia after vaping and to better characterize the lung inflammation we observed. Serum proteomics will be assessed using recent quantitative sequential window acquisition of all theoretical fragment-ion spectra (SWATH) liquid chromatography/mass spectrometry (ULB – Faculty of Medicine - Pr [name]). It allows reproducible identification and accurate quantification of thousands of proteins from complex protein mixtures with performance characteristics that approach those of multiple/selected reaction monitoring. Fragment ion spectra from all measurable peptides of a digested proteome are generated through a data-independent acquisition with a much lower ion suppression effect between signals. Moreover, once acquired, the data can be perpetually

analyzed in silico to test new potential biomarkers.²¹ The relative quantification of proteins in the serum and the assessment of their potential post-translational modifications between experimental sessions and groups (e-cigarettes users and non-smokers-non-e-cigarettes users) will allow to discover new biomarkers associated with e-cigarettes vaping. Furthermore, the concentrations of these newly discovered biomarkers will be measured in the serum and urine by using dedicated commercial ELISA kits (or by Western blotting followed by immunodetection).

3.3.12 Serum, urine and breath exhaled condensate metabolomics analysis

In order to better understand effects of regular e-cigarettes consumption on human metabolome and to confirm vaping cessation, serum, urine and breath exhaled condensate of our participants will undergo metabolomics analysis. This will be done using nuclear magnetic resonance spectrometry at the Department of Human Biology & Toxicology (University of Mons - Faculty of Medicine – Pr. [name]) as previously described.²²

3.3.13 Sample size calculation

The primary objective of this study is to determine whether e-cigarette vaping cessation for five days increases transcutaneous oxygen partial pressure in regular users. Based on our previous researches, we assume that baseline mean transcutaneous oxygen partial pressure will be 80 mm Hg with a standard deviation of 7 mm Hg. To demonstrate that e-cigarette vaping cessation for five days significantly increases transcutaneous oxygen partial pressure, we assume a minimal rise in transcutaneous oxygen partial pressure of 10 mm Hg. We will need 16 patients, with 80% power to detect a group difference of 10 mm Hg in the change of transcutaneous oxygen partial pressure at a two-sided alpha-level of 0.05. We will enroll 21

participants in order to be sure to achieve a sufficient statistical power.

4. References

5. Etter JF. Throat hit in users of the electronic cigarette: An exploratory study. *Psychol Addict Behav*. 2016;30:93-100
7. Marseglia GL, Cirillo I, Vizzaccaro A, Klersy C, Tosca MA, La Rosa M, Marseglia A, Licari A, Leone M, Ciprandi G. Role of forced expiratory flow at 25-75% as an early

marker of small airways impairment in subjects with allergic rhinitis. *Allergy Asthma Proc.* 2007;28:74-8

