A. In comparison to pursuit of PG/GLY vaping with or without nicotine, e-cigarette cessation for five days:

- Increases transcutaneous O₂ tension and O₂-haemoglobin saturation
- Decreases respiratory rhythm
- Increases lung diffusing capacities and forced expiratory flows
- Increases maximal rate of oxygen consumption during cycle ergospirometer test
- Modifies heart rate variability
- Decreases arterial stiffness
- Decreases serum PG/GLY and nicotine concentrations

B. In comparison to PG/GLY vaping with nicotine, e-cigarette cessation for five days or PG/GLY vaping:

- Increase cutaneous vascular conductance and decrease arterial stiffness
- Increase acetylcholine and heat mediated vasodilation

C. Each of the three experimental sessions (e-cigarette cessation, PG/GLY vaping and pursuit regular consumptions):

- Induces specific serum, urine and exhaled breath condensate metabolomics profiles
- Induces specific serum proteomics profile

This research proposal tests also the following hypothesis regarding acute effects of PG/GLY vaping with and without nicotine in regular e-cigarettes users:

A. In comparison to baseline, PG/GLY vaping without nicotine:

- Decreases transcutaneous O₂ tension and O₂-haemoglobin saturation
- Increases respiratory rhythm
- Increases serum PG/GLY concentrations
- Induces specific serum, urine and exhaled breath condensate metabolomics profiles

B. In comparison to baseline and PG/GLY without nicotine, PG/GLY vaping with nicotine:

- Decreases transcutaneous O₂ tension and O₂-haemoglobin saturation
- Decrease continuous vascular conductance and increase arterial stiffness
- Increases respiratory rhythm
- Increases serum PG/GLY and nicotine concentrations
- Induces specific serum, urine and exhaled breath condensate metabolomics profiles

3. Methodology

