3.1. Participants, interventions, periods and randomization

The participants, who are exclusive vapers since at least one years, will undergo three experimental periods in a random order: e-cigarettes cessation for five days (**cessation session**), nicotine free vaping for five days (**nicotine free session**), regular e-cigarettes consumption (**regular consumption session**). Baseline clinical cardiorespiratory parameters will be assessed at the start of each of the 3 experimental sessions. The participants will, then, vape sham-puffs (**cessation session**), nicotine free-puffs (**nicotine free session**) and

nicotine puffs (**regular consumption session**). During acute exposition, we will monitor at each puff any feelings of throat irritation, burn taste and Borg perception scale items (cough, chest tightness, breathlessness, secretions and wheezing). This acute exposition will be followed by clinical cardiorespiratory parameters assessment, lung function tests and maximal cycle ergometer test.

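### The sample size of 16 rests on a group comparison and a baseline SD, but the trial is a three-period crossover; the calculation should be restated within participants, with enrolment left at 21

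*Combined protocol and SAP*

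**What the plan says.** Section 3.3.13 gives the primary objective as to "determine whether e-cigarette vaping cessation for five days increases transcutaneous oxygen partial pressure in regular users". Its inputs are a "baseline mean transcutaneous oxygen partial pressure will be 80 mm Hg with a standard deviation of 7 mm Hg", and for the effect, "we assume a minimal rise in transcutaneous oxygen partial pressure of 10 mm Hg". It concludes: "We will need 16 patients, with 80% power to detect a group difference of 10 mm Hg". The same sentence places this difference on the scale of a change and sets alpha at 0.05, two-sided. Enrolment is then set at 21, with no loss rate given.

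Section 3.1 describes the design: participants "will undergo three experimental periods in a random order". The periods are cessation, nicotine-free vaping and regular consumption. The goals in section 2 set cessation against continued vaping with or without nicotine. Section 3.3.13 does not say which of those sessions is the primary comparator.

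The plan gives no formula, test, SD of a change, SD of a between-session difference or between-session correlation.

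**The concern.** In a crossover each participant is compared with himself or herself, so the standard error of the primary contrast depends on the SD of the within-participant difference between sessions. An SD attached to a baseline mean describes how participants differ from one another. It says nothing about that difference until a correlation is added. Section 3.3.13 uses the baseline SD directly and speaks of a group difference, which is the language of a parallel-group trial.

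This is the plan's only power statement, and it supports the primary objective. If formula and variance belong to another design, the stated 80% is not the trial's power and 10 mm Hg is not the difference it can detect at that power. The true figures could lie on either side, depending on a variance that the plan leaves out.

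**Working it through.** **Inputs from section 3.3.13.** Difference 10 mm Hg; SD 7 mm Hg at baseline; two-sided alpha 0.05; power 80%; 16 needed, 21 enrolled. **Assumption, because the documents give none:** the correlation between measurements in the same person, taken as zero or more.

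**1. Reproducing 16.** (1.960 + 0.842)² = 7.849. For two independent groups by the normal approximation, n per group = 2 × (7/10)² × 7.849 = 7.69, so 8 per group and 16 in total. This matches the stated number. By an exact two-sample t-test, 8 per group gives 75.7% power and 9 per group (18 in total) are needed for 80%.

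If 7 is instead taken as the SD of the paired difference, n = (7/10)² × 7.849 = 3.85, so 4 by the normal approximation, or 7 by the t-test. That does not reproduce 16.

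**2. Paired contrast on session values.** SD of the difference = 7 × √(2(1 − ρ)).
- ρ = 0: SD = 7 × √2 = 9.90.
- ρ = 0.5: SD = 7 × √1 = 7.0.

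**3. Difference between sessions of within-session changes.** Section 3.3.13 refers to change, so this reading needs checking. Four measurements enter. With all correlations zero, SD = √(4 × 7²) = 14. The normal approximation then gives (14/10)² × 7.849 = 15.4, so 16; the paired t-test needs 18. With a before–after correlation of 0.1 and none between the two changes, SD = 14 × √0.9 = 13.28, and the paired t-test needs 16, with 80.4% power. With a correlation of 0.5 either within sessions or between changes, SD falls to 14 × √0.5 = 9.90, and 10 are needed. So this reading returns about 16 only when the SD of the difference is about 13 to 14 mm Hg, that is, with correlations near zero.

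**4. Results by paired t-test (noncentral t), difference 10 mm Hg.** Detectable differences are at 80% power.

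| SD of difference (mm Hg) | Arises from | N for 80% | Power at 16 | Power at 21 | Detectable at 16 (mm Hg) | Detectable at 21 (mm Hg) |
|---|---|---|---|---|---|---|
| 7.0 | session values, ρ = 0.5 | 7 | >99.9% | >99.9% | 5.2 | 4.5 |
| 9.9 | session values, ρ = 0 | 10 | 96.5% | 99.3% | 7.4 | 6.4 |
| 14.0 | changes, all correlations 0 | 18 | 76.1% | 87.5% | 10.5 | 9.0 |

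**5. Largest SD of the difference that keeps 80% power for 10 mm Hg.** With 16 participants it is 13.34, so 13.3 rounded down. With 21 it is 15.56, so 15.5 rounded down; at 15.6 power is 79.8%.

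**6. Two comparators.** If alpha were split over both vaping sessions (0.025 each), the paired contrast on session values would need 12 participants at ρ = 0 and 8 at ρ = 0.5, still below 16.

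These figures ignore the few degrees of freedom that period effects would use.

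**The case against.** The strongest reply is that nothing about the trial's size needs to change, and that the two-group origin is a guess. Much of this stands.

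- **The formula is inferred.** The plan names none. The exact match, the reference to groups and the baseline SD all point to two independent groups, but a difference of changes also reaches about 16. That route need not discard the pairing completely: at a correlation of 0.1 it gives 16 participants and 80.4% by t-test. It does require an SD of the difference of about 13 to 14 mm Hg, which the plan neither states nor supports.
- **The gap between 75.7% and 80% is minor.** For two groups of 8 it is the usual difference between the normal approximation and the t-test. It is worth about two participants, which enrolling 21 covers.

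A reader might infer that the trial is underpowered. The documents do not support that. On session values with a correlation of zero or more, 16 is conservative. In the least favourable case worked here (SD 14), the shortfall appears at 16 and is gone at 21. Section 3.2 discards the whole dataset of a participant who violates the protocol, so the analysable number may fall below 21, but at SD 14 18 participants still suffice for 80%.

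A reader might also infer that a null result could not be interpreted. That does not follow. A null result is read from the confidence interval for the observed within-participant difference, which uses the observed variance and not the planning SD.

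What remains is that the stated power does not follow from the stated inputs for this design.

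**Conclusion.** The point holds as a should-fix correction to the sample size section. The stated 16 for 80% power uses a baseline SD and the wording of a group comparison in a trial without groups, and the SD that matters is absent. With SD 7 and a correlation of zero or more, a paired contrast on session values needs at most 10 participants, and 16 give at least 96.5% power. If the endpoint is a difference of changes and correlations are near zero, 16 is about right or slightly short.

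Across the scenarios shown, the difference detectable with 21 participants runs from 4.5 to 9.0 mm Hg, always below the planned 10. The mismatch therefore makes the power statement unreliable without showing that the trial is too small. The range rests on assumed correlations and on SD 7 applying at every measurement. Neither can be checked from the documents.

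**What to change.** Rewrite section 3.3.13 as a within-participant calculation:

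1. Replace the reference to a group difference with a within-participant difference between sessions. Name the comparator session, and say whether the outcome is a session value or a within-session change.
2. Take the SD of that difference from the sponsor's earlier repeated-session recordings (the section already draws on the sponsor's previous research) and state the source.
3. Restate power and detectable difference by paired t-test for 16 and for 21 analysable participants.
4. If that SD is not available, state that 80% power for 10 mm Hg at two-sided 0.05 holds for an SD of the difference up to 13.3 mm Hg with 16 participants, or 15.5 mm Hg with 21.

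The cost is the wording of one section and a look at existing data. Enrolment stays at 21, and no procedure changes.
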